CLINICAL TRIAL DOCUMENT COVER PAGE

Official Title of the Study:

Adherence to the Mediterranean Diet Following Nutritional Education and Its Effect on Anxiety, Depression, Fatigue, and Sleep Quality Among a Group of Lactating Women in Jordan: An Interventional Study

NCT Number: Not yet assigned

Document Type: Protocol / Statistical Analysis Plan

Version Number: Version 1.0

Document Date: May 2026

Sponsor / Institution: Applied Science Private University

Principal Investigator: [name]

Contact Information: [contact]

Title of the project

Adherence to the Mediterranean Diet Following Nutritional Education and Its Effect on Anxiety, Depression, Fatigue, and Sleep Quality Among a Group of Lactating Women in Jordan: An Interventional Study.

The outcome:

The aim of our study is to compare the degree of adherence to MedDiet between women who received educational and nutritional interventions during 6 months of follow-up and those without such interventions, and to examine the impact of these interventions on mothers' nutritional status, anthropometrics, and mental health.

The objectives:

The objectives of the current study are:

1. Investigate the impact of an educational intervention on MedDiet among a group of lactating women aged 18-40 years and above in Jordan over a six-month follow-up period.
2. Investigate the relationship between MedDiet adherence, obesity, and mental health. among a group of lactating women aged 18-40 years and above in Jordan over a six-month follow-up period.

Protocol**Study design and setting**

An intervention study is conducted for lactating mothers with follow-up at 3 and 6 months. Participant recruitment focuses on lactating women with infants aged 1-2 months.

The study is conducted at the Ministry of Health's childbirth vaccination clinics in Amman and Irbid, Jordan. The clinics have a fine reputation for maternal and child health services with organized working and research systems.

Ethical considerations

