- **A diet quality questionnaire,** the food-based diet quality index, was created by synthesizing current nutrition knowledge. The questionnaire includes 14 "healthy" and 7 "unhealthy" food components known to affect health and prevent major diet-related diseases (Kronsteiner-Gicevic et al., 2021).
- **Depression, Anxiety, and Stress Scale-21 Items (DASS-21)** is a set of three self-report scales developed to measure the emotional states of depression, anxiety, and stress that can effectively assess mental health symptoms for individuals (Bryson et al., 2021; Effati-Daryani et al., 2020; Khouj et al., 2022).
- **Modified Fatigue Impact Scale (MFIS):** The MFIS is a modified version of the FIS that measures physical, cognitive, and psychosocial fatigue. Participants rate the impact of fatigue on their lives over the past 4 weeks on a scale of 0 (no problem) to 4 (extreme problem) (Strober et al., 2020).
- **The Pittsburgh Sleep Quality Index (PSQI)** measures general sleep quality and is a recommended questionnaire for studying global sleep and insomnia symptoms (Zitser et al., 2022).
- **The Beck Depression Inventory (BDII):** This depression self-report measure has been extensively researched and used in clinical and non-clinical populations. It has strong psychometric properties and is widely implemented in depression-related research (Arnarson et al., 2008).
- **SF-36 ARABIC**

B. Educational Intervention:

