Descriptive statistics and correlations for all quantitative and categorical study variables are calculated at baseline and at the end of the study to present the prevalence of depression, anxiety, and stress severity. Appropriate descriptive statistics such as percentages, means, and standard deviation summarize the data depending on the variable type. The Shapiro–Wilk test will be applied to assess data normality. Data are described using means (SD) and percentages. The student's t-test will be used to compare the means and medians of independent variables between groups; Pearson's Chi-Square test will be used for categorical data to test for association and probability, especially the relationship between sociodemographic variables, nutritional status, and the severity of depression, anxiety, and stress. Moreover, the significance level was set at $p < 0.05$, along with logistic regression, to identify the determinants of the severity of depression, anxiety, and stress among pregnant women attending the clinics. For the ordinal regression modeling, the severity is coded as normal = 0, mild = 1, moderate = 2, and severe = 3. The multivariable ordinal logistic regression model includes Variables statistically significant at $P \leq 0.05$ in the bivariate analyses.

References:

- Arnarson, P. Ö., Ólason, D. P., Smári, J., & Sigurdsson, J. F. (2008). The Beck Depression Inventory Second Edition (BDI-II): Psychometric properties in Icelandic student and patient populations. *Nordic Journal of Psychiatry*, 62(5), 360–365. <https://doi.org/10.1080/08039480801962681>

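### The severity model's only entry rule is a bivariate P value, so other symptom scales can enter as determinants and weaken the diet and obesity associations that objective 2 asks about

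*Combined protocol and SAP*

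**What the plan says.** The second objective is to "Investigate the relationship between MedDiet adherence, obesity, and mental health" in lactating women over six months.

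Statistical analysis describes one kind of multivariable model, an ordinal logistic regression in which "the severity is coded as normal = 0, mild = 1, moderate = 2, and severe = 3". Regression is to be used "to identify the determinants of the severity of depression, anxiety, and stress". The entry rule is a single sentence: "The multivariable ordinal logistic regression model includes Variables statistically significant" at P ≤ 0.05 in the bivariate analyses.

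Two other sentences bear on which variables could be candidates:
- The chi-square test is to be used for categorical data, "especially the relationship between sociodemographic variables, nutritional status, and the severity of depression, anxiety, and stress".
- "Descriptive statistics and correlations for all quantitative and categorical study variables are calculated at baseline and at the end of the study", with the stated purpose of presenting the prevalence of severity.

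Under A. Questionnaires, the same women complete the MEDAS, the DASS-21 (depression, anxiety, stress), the MFIS, the PSQI, the SF-36 and the Beck inventory. Of the last, the plan notes that "This depression self-report measure has been extensively researched". Fatigue and sleep quality are named as outcomes in the study title.

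**The concern.** A rule based only on P values favours the variables most strongly related to the outcome. For a DASS-21 severity class, these are likely to be a second depression scale, the two sibling DASS-21 scales, and the sleep, fatigue and health-status scores from the same interviews. Nothing in the rule keeps them out, and nothing keeps MEDAS or BMI in.

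Once such scales are in the model, the MEDAS coefficient measures the association with depression severity that remains after other measures of distress have been accounted for. Objective 2 does not ask that question. If diet works through general distress, or through sleep and fatigue, part of its association is adjusted away. A small, non-significant coefficient could then be read as showing that diet is unrelated to mood, while the reported determinants of depression would be other symptom scores.

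**Working it through.** **Step 1. What the text allows.** The entry rule names no candidates, exclusions or forced terms. The word *especially* in the chi-square sentence gives emphasis but excludes nothing, and it belongs to that test rather than to the regression. The rule therefore permits the scales to enter, but the plan does not say that they will.

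**Step 2. No planned figure to reproduce.** The plan gives no number for this model. From Sample size, only 180 women and 20% non-response are used: 180 × (1 − 0.20) = 144.

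**Step 3. Simulation A (assumed inputs).** A latent depression score is driven by MEDAS (r = −0.25). DASS depression and Beck correlate 0.8; anxiety and stress 0.65; sleep and fatigue 0.5. Severity classes are 60/20/14/6%. Proportional-odds models were fitted with MEDAS alone and with every scale passing P ≤ 0.05, with 300 runs per scenario. The SF-36 was not included. Loss = 1 − (adjusted coefficient ÷ coefficient alone).

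| Scales available | n | Log OR per SD, alone | Log OR per SD, adjusted | Loss | Power, alone → adjusted |
|---|---|---|---|---|---|
| All five | 144 | −0.394 | −0.114 | 1 − 0.114/0.394 = 71% | 62% → 10% |
| All five | 180 | −0.385 | −0.087 | 1 − 0.087/0.385 = 77% | 72% → 9% |
| Without Beck | 144 | −0.398 | −0.154 | 1 − 0.154/0.398 = 61% | 65% → 13% |
| Sleep and fatigue only | 144 | −0.393 | −0.270 | 1 − 0.270/0.393 = 31% | 61% → 28% |

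In the first row, the odds ratio per SD moves from exp(−0.394) = 0.67 to exp(−0.114) = 0.89.

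**Step 4. Simulation B (different assumptions).** Latent distress D correlates −0.2 or −0.3 with diet. Four scales correlate with D as listed. The severity score correlates 0.9 with D, and classes are 55/15/17/13%. Screening was by Spearman P ≤ 0.05, at n = 144 and 180, with 200 runs per scenario (Monte Carlo error up to √(0.25/200) = 3.5 percentage points).

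| Scale–distress correlations | Loss in diet log OR | Power, alone | Power, adjusted |
|---|---|---|---|
| 0.4, 0.4, 0.4, 0.5 | 27–29% | 49–90% | 28–56% |
| 0.5, 0.5, 0.6, 0.7 | 46–49% | 45–90% | 14–35% |
| 0.6, 0.6, 0.7, 0.8 | 62–67% | 47–89% | 10–14% |

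The scales passed the screen in 96–100% of cases. Diet passed in only 40–89% of runs, so the rule can also drop the exposure before any adjustment.

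**Step 5. Closed-form check of Simulation B.** Let ρ be the diet–distress correlation, S = Σ r²/(1 − r²) over the scales, and v = 1 − ρ². On the latent scale, the fraction of the diet coefficient retained is k = 1/(1 + vS). The log odds ratio also rescales with the residual SD, by √[(0.81v + 0.19)/(0.81V + 0.19)], where V = 1/(1/v + S).

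For ρ = −0.2, v = 0.96:
- Weakest scales: S = 3(0.16/0.84) + 0.25/0.75 = 0.905; k = 0.535; V = 0.514; rescaling √(0.968/0.606) = 1.26; loss = 1 − 0.535 × 1.26 = 32%.
- Strongest scales: S = 2(0.36/0.64) + 0.49/0.51 + 0.64/0.36 = 3.864; k = 0.212; V = 0.204; rescaling √(0.968/0.355) = 1.65; loss = 1 − 0.212 × 1.65 = 65%.

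These approximations lie close to the simulated 27–28% and 62–67% at ρ = −0.2. The loss depends almost wholly on S, that is, on how well the admitted scales measure the same distress.

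**The case against.** - **Entry is not stated.** No sentence names a symptom scale as a predictor of severity. Where the plan says what is compared with severity, it names sociodemographic variables and nutritional status, and under Instruments it lists abuse as a possible confounder, apart from the outcome scales. This stands. A reader might infer that the plan puts these scales into the model and that masking will follow; the documents support only that the rule allows it.
- **The sentence covering all study variables is descriptive.** Its stated purpose is to present prevalence, and it is not identified as the screen for the regression. This also stands. The point rests on the open entry rule, not on that sentence.
- **Objective 2 is not left without an analysis.** The same sentence would yield unadjusted MEDAS and BMI correlations with the DASS-21 scores, and the plan does not expressly tie the ordinal model to objective 2. Both are true. But this is the only multivariable model described, so it is the natural source for an adjusted answer.
- **The size follows from chosen inputs.** Both simulations let diet act on severity only through distress that the scales also measure, which builds in attenuation. The largest losses need all five scales to enter, including a second depression inventory as a predictor of depression. This stands: a loss of around 70% is not a forecast.
- **Sleep and fatigue may be causes of mood.** Excluding them is partly a causal judgement. That is fair, and a labelled exploratory model meets it.

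**Conclusion.** The concern holds as a defect in a stated rule. Followed literally, the rule can admit proxies of the outcome and sibling outcomes, and the adjusted diet coefficient then no longer answers objective 2. The sponsor should correct it.

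Across the assumed scenarios, the MEDAS log odds ratio shrinks by 27% to 77%, and power falls from 45–90% to 9–56%. The low end corresponds to weakly correlated scales, or to sleep and fatigue alone (31%); the high end to all five scales entering. The direction was the same in every scenario, but the size rests wholly on correlations that the documents do not give.

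Obesity was not simulated; the argument there is by the same logic only. Nor do the documents support a prediction that the trial will conclude that diet is unrelated to mood, since unadjusted correlations would still be available.

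**What to change.** Replace the entry-rule sentence under Statistical analysis with:

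*Each severity model includes MEDAS score, BMI and study group whatever their bivariate P value, plus a prespecified list of sociodemographic variables, smoking and abuse. Other outcome scales (Beck inventory, other DASS-21 scales, PSQI, MFIS, SF-36) are not eligible as predictors in these models; associations among scales are reported separately as correlations, and any model adding sleep or fatigue is labelled exploratory.*

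The list should name each variable and say which BMI is meant, since Instruments mentions both pre-pregnancy BMI and anthropometry. Study group is there for adjustment: with MEDAS in the same model, its coefficient does not estimate the effect of the educational intervention.

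The cost is a short text change, with no new data or sample size. Apparent model fit will be lower, and sleep and fatigue will not be assessed as determinants in the main model. If the sponsor never meant the symptom scales to be candidates, the change simply records that.
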